7.6.2 Clinical Laboratory Parameters

Blood

Clinical laboratory data (CBC with differential, serum chemistry) may be presented graphically for selected lab tests by scheduled visit. Summary statistics may be tabulated where appropriate. The worst post baseline NCI CTCAE v4.03 grade will be presented for each lab test.

Laboratory results and NCI CTCAE grades for hematology, and serum chemistry will be presented in data listings. All laboratory data will be presented in conventional units.

Urine

UPC ratio will be presented graphically by scheduled visit. All other urine parameters will be listed.

7.6.3 ECOG Performance Status

Shifts from baseline to the best and worst post-baseline score will be tabulated.

7.6.4 Vital Signs

Vital sign measurements (systolic and diastolic blood pressure, heart rate, and body temperature) will be listed by patient for each time point and presented graphically for each vital sign by scheduled visit.

7.6.5 Concomitant Medications

Concomitant medications with WHO Drug substance name will be listed by patient. Transfusion, G-CSF administration, systemic steroids, and ocular interventions will be summarized and listed as appropriate.

7.6.6 Additional Safety Analyses

7.6.6.1 Ocular Examination Results

Ocular examination results will be presented in data listings. The improvement/resolution of corneal AEs may also be explored through visual acuity exam results.

7.6.6.2 Patient-Reported Health Outcome (VFQ-25)

VFQ-25 composite score and select sub-scale scores may be summarized with descriptive statistics. The derivation of the composite score and sub-scale scores are specified in Appendix C. Scores and the change from baseline may be listed or tabulated. The relationship between ocular AEs and VFQ-25 scores may be explored.

7.6.6.3 Electrocardiogram (ECG)

ECG status (normal, abnormal clinically significant, or abnormal not clinically significant) at EOT and shift from baseline will be summarized.

7.6.6.4 Transplant-Related Information Following ASCT

The incidence of post-transplant viral reactivation and infections will be listed and summarized for patients who received ASCT. The duration from stem cell infusion to neutrophil and platelet engraftment will also be listed and summarized.

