1.4 Rationale for Study

As described above, novel treatment strategies are needed to improve outcomes for relapsed, transplant-eligible DLBCL patients, where the goal is to achieve a high-quality remission that enables subsequent ASCT. The primary unmet need is the failure to achieve a high rate

of CR, as achievement of a PET-negative CR following second-line salvage therapy has been associated with improvement in outcome in relapsed DLBCL patients who proceed to ASCT (Dickinson 2010; Johnston 2008; Terasawa 2010).

Preliminary activity has been observed with denintuzumab mafodotin monotherapy in patients with relapsed or refractory DLBCL after failure of second-line salvage (unless transplant-ineligible) and beyond (Moskowitz 2014). Introduction of denintuzumab mafodotin into second-line treatment may be both clinically meaningful and associated with a favorable risk-benefit ratio. Denintuzumab mafodotin has not previously been combined with RICE. However, given the known safety profiles of RICE and denintuzumab mafodotin alone, few overlapping toxicities are anticipated. Safety data to date in Protocol SGN19A-002 have shown a favorable toxicity profile for denintuzumab mafodotin, with hematopoietic toxicity and peripheral neuropathy uncommon (Moskowitz 2014). Although myelosuppression is an expected consequence of RICE therapy, only transient thrombocytopenia that recovered prior to the subsequent 3-week cycle has been consistently associated with treatment with denintuzumab mafodotin in the NHL population.

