9.3.1.3 Handling of Dropouts and Missing Data

Missing data will not be imputed, with the exception of AE dates while calculating duration of events and treatment emergent status. Patients with missing values of a variable other than response endpoints (CR and OR) and time-to-event endpoints (PFS, duration of response, and OS) will be excluded from the analysis of that endpoint. Patients whose disease response cannot be assessed will be scored as non-responders for calculating the response rate (CR rate and ORR). Censoring rules will be applied to the estimation of the distribution of the time-to-event endpoints, details will be provided in the SAP.

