9.3.9.5 Other Safety Analyses

Vital Signs

Vital signs will be presented graphically for each vital sign by scheduled visit. Summary statistics and change from baseline and/or predose to postdose may be tabulated where appropriate.

ECOG Status

ECOG status may be summarized for each visit. Shifts from baseline to the best and worst postbaseline score may be tabulated.

ECG

ECG status (normal, abnormal clinically significant, or abnormal not clinically significant) may be summarized for each scheduled ECG, and shifts from baseline may be tabulated.

Ocular Toxicities

Patient incidence of ocular toxicities (as defined by the MedDRA system organ class [SOC] of eye disorders or custom queries) will be presented by treatment arm. Additional analyses may be done, including incidence of ocular toxicities by maximum severity, ocular toxicities that lead to treatment discontinuation, etc.

Transplant-Related Information Following ASCT

Time to neutrophil and platelet engraftment may be summarized and tabulated where appropriate.

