- U In each treatment arm, additional transplant-related data will be collected following ASCT until time of engraftment and will include, but not be limited to, the time to neutrophil and platelet engraftment.
- V Cycle 1 only. Blood samples for PK and biomarker testing (Table 3).
- W Cycle 1 and Cycle 2 only. Only for patients not continuing on treatment or not starting the next cycle on Day 22. Blood sample for PK testing (Table 3).
- X saAPI for patients aged ≤ 60 years, and standard IPI for patients aged >60 years (Appendix D).
- Y For both treatment arms, RICE administration to occur on Days 1–3 (± 1 day).
- Z Weight not required.
- AA Fasting blood glucose at baseline.

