6.5 Handling of Dropouts and Missing Data

With the exception of the scenarios covered in this section, missing data will not be imputed.

AE dates will be imputed for the purpose of calculating duration of events and treatment-emergent status (see Appendix A for imputation details and Appendix B for treatment-emergent definition). Censoring will be described in Section 7 with each planned analysis, as applicable.

Unless otherwise specified, lab values which are recorded or provided as being less than x.x will be included in figures and summaries as x.x/2. For the purpose of grading, lab values reported as less than x.x will be imputed as x.x.

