7.6.1.1.1 Ocular AEs

Incidence, onset and improvement/resolution of ocular AEs of interest will be summarized based on the safety analysis set. The ocular AEs of interest will be defined by Standardised MedDRA Queries (SMQs) or Sponsor Specified Queries (SSQs) as appropriate. The

definition of the SSQs will be maintained in a separate document and will be finalized prior to database lock.

Patient incidence of treatment-emergent ocular AEs of interest will be presented by system organ class, preferred term and maximum severity. Ocular AEs leading to treatment discontinuation will be summarized.

Time to onset and duration to improvement or resolution will be summarized at the patient level for ocular AEs.

Date of onset is defined as the date of earliest occurrence of events of interest. Time to onset for will be summarized by descriptive statistics.

Improvement and resolution of ocular AEs will be derived per patient level. The date of resolution is defined as the earliest time that the patient does not have any ongoing ocular events (i.e. all events with outcome of resolved/recovered or resolved/recovered with sequelae, or all events with severity decreasing to baseline condition or better).

Improvement of ocular AEs is defined based on the worst grade for each patient. If a patient has worst grade 3 or 4 events, date of improvement or resolution is defined as the earliest date that the patient does not have any ongoing grade 3 or 4 events (i.e. the worst grade the patient is experiencing is 2 or below). If a patient has worst grade 2 ocular events of interest, the date of improvement or resolution is defined as the earliest date that the patient does not have any ongoing grade 2 events (i.e. the worst grade the patient is experiencing is 1 or below).

Time to improvement and resolution from first onset and from last treatment of 19A will be summarized for the patients who experienced ocular AEs of interest. Duration of ocular AEs may be summarized by Kaplan-Meier methodology. If a patient does not experience an improvement or resolution, the patient will be censored at last contact date for ocular symptoms, and censored at the date of last ophthalmology exam for corneal findings.

The relationship between ocular AEs and ocular interventions may be explored.

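### The planned summary of time to neutrophil and platelet engraftment has no rule for transplanted patients who die first or never engraft, so as written it would describe engrafted patients only

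*SAP*

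**What the plan says.** The protocol synopsis and Section 7.7 place time to neutrophil and platelet engraftment, in each arm, among the transplant data gathered under the safety assessments. Protocol 6.7 and Appendix A collect it for patients who go on to ASCT.

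The analysis text is short. SAP 7.6.6.4: "The duration from stem cell infusion to neutrophil and platelet engraftment will also be listed and summarized". Protocol 9.3.9.5: "Time to neutrophil and platelet engraftment may be summarized and tabulated where appropriate". SAP 6.1 makes mean, median, standard deviation, minimum and maximum the default for continuous variables, presented by arm.

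Two general rules bear on patients without an engraftment date:

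- Protocol 9.3.1.3 covers patients with a missing value on a variable other than the response endpoints (CR and OR) "and time-to-event endpoints (PFS, duration of response, and OS) will be excluded from the analysis of that endpoint". The bracketed endpoints are exceptions to the exclusion. Engraftment is not among them.
- SAP 6.5 imputes only AE dates and below-limit laboratory values, and adds: "Censoring will be described in Section 7 with each planned analysis, as applicable". Section 7.6.6.4 describes no censoring.

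For ocular AEs the SAP does supply a rule (7.6.1.1.1). It allows Kaplan-Meier estimation of duration and says: "If a patient does not experience an improvement or resolution, the patient will be censored at last contact date for ocular symptoms".

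**The concern.** Engraftment time is defined only for patients who engraft. A patient who dies first, or whose counts never recover, has no duration to enter in a table of means and medians. If such patients drop out, the table describes the speed of recovery among those who recovered and says nothing about how many did. Two arms with the same times among engrafted patients would show the same table even if one had several failures and the other none.

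What is at stake is one descriptive safety comparison: whether adding the study drug to RICE leaves patients with poorer marrow recovery after transplant. A summary that cannot register failure cannot answer that.

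**Working it through.** **Text check.** The documents state no figure for engraftment, so there is none to reproduce. Taking the texts in order:

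1. SAP 7.6.6.4 names no estimator, censoring date, competing event or denominator for engraftment time.
2. SAP 6.5 sends the reader to Section 7 for censoring, and 7.6.6.4 has none.
3. Protocol 9.3.1.3 excludes missing values except for CR, OR, PFS, duration of response and OS. SAP 9.1 declares no change from the protocol.
4. Even without step 3, the SAP 6.1 descriptive statistics can be computed only on patients who have a duration.

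Steps 1 to 4 lead to a summary of engrafted patients only.

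**Whether other outputs fill the gap.** SAP 7.6.7 counts and lists deaths, split at 30 days from last study treatment and not by engraftment status. SAP 7.5.2.7 gives the number transplanted. Protocol 7.7.1.3 ends routine AE reporting at the later of the EOT visit and 30 days after last treatment. With RICE typically finishing on Day 3 of Cycle 3, 30 days later is about Day 33. Protocol 3.1 recommends ASCT within 8 weeks of Cycle 3 Day 1, which is 8 × 7 = 56 days. Engraftment can therefore fall after routine AE reporting has closed. From then on, only SAEs judged related to study treatment must be reported.

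**Illustration.** Inputs:

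- 50 patients per arm (SAP 6.2).
- 50% reach ASCT, the share Protocol 1.1 reports for a large randomised salvage trial. So 50 × 0.5 = 25 per arm. This is an assumption for the present trial.
- Among engrafted patients, times are lognormal with median 20 days and log-SD 0.35. This is assumed.
- k of 25 never engraft or die first, with f = k/25. This is assumed.

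Among engrafted patients, F(t) = Φ[(ln t − ln 20)/0.35]. At day 28, chosen only for illustration, F = Φ(0.3365/0.35) = Φ(0.961) = 0.832.

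With all ASCT patients kept, cumulative incidence is (1 − f) × F(t). Its median is 20 × exp{0.35 × z[0.5/(1 − f)]}, where z is the standard normal quantile.

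| Failures k of 25 | f | Engrafted only: median, by day 28 | All ASCT patients: median, by day 28 |
|---|---|---|---|
| 0 | 0% | 20.0 d, 83% | 20.0 d, 83% |
| 1 | 4% | 20.0 d, 83% | 20.4 d, 80% |
| 2 | 8% | 20.0 d, 83% | 20.8 d, 77% |
| 3 | 12% | 20.0 d, 83% | 21.2 d, 73% |
| 5 | 20% | 20.0 d, 83% | 22.4 d, 67% |
| 8 | 32% | 20.0 d, 83% | 24.9 d, 57% |

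For k = 3: 0.5/0.88 = 0.568, z = 0.172, and 20 × exp(0.060) = 21.2 days; 0.88 × 0.832 = 0.732.

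The engrafted-only column is constant by construction. For 1 to 3 failures the all-patient median moves by about a day at most, while the proportion engrafted by day 28 falls by 3 to 10 percentage points. The count of failures carries most of the information.

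**The case against.** The strongest reply is that no sentence in either document says engraftment is summarised only where a date exists. Protocol 9.3.1.3 speaks of missing values and of endpoints. Engraftment time is not a listed endpoint, and an event that has not happened is not plainly a missing value. The SAP, which is the fuller plan, does not repeat the exclusion. This stands to the extent that the exclusion is inferred. It does not rescue the analysis, because no other rule is given and the default statistics need a duration. SAP 6.1 also mentions Kaplan-Meier, but for median survival time; 7.6.6.4 does not invoke it or say how a death would be treated.

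A reader might go further and infer that failed engraftment and early transplant death disappear from the safety results altogether. The documents do not support that. Deaths are counted, summarised by cause and listed, OS is analysed from randomisation, ASCT receipt is summarised, and the engraftment listing may show a blank. A careful reader could compare the number transplanted with the number in the engraftment table, but could not tell from the summaries whether a gap was death, graft failure or an unrecorded date.

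A reader might also take the thrombocytopenia in Protocol 1.4 as a reason to expect poor engraftment. That section says "only transient thrombocytopenia that recovered prior to the subsequent 3-week cycle has been consistently associated with treatment with denintuzumab mafodotin". It describes an effect that resolved, offers it as reassurance and draws no link to recovery after transplant. The stem-cell question the plan does make a secondary endpoint, mobilisation, uses the total number of patients as its denominator (Protocol 9.2.2.4).

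**Conclusion.** The point holds for the engraftment summary and no further. As written, the summary by arm would describe engrafted patients only. For given times among those patients, it would not move with the number who fail or die first. This is more than missing detail: following the text gives a table that cannot show the harm it is there to monitor, and the SAP already handles the same data structure properly for ocular AEs.

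The size is unknown, because the documents give no rate of failed engraftment. One to three failures among an assumed 25 transplanted patients per arm is 4% to 12%. The wider contrast in the table needs 8 of 25 failures and shows only the direction of the effect. The item is descriptive and untested, so CR rate, PFS and duration of CR are unaffected. It should be corrected, but it does not threaten the trial's main conclusions.

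**What to change.** In SAP 7.6.6.4:

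1. Use all patients who received ASCT as the denominator, by arm.
2. Tabulate the number and percentage engrafted, not engrafted and dead before engraftment by a pre-specified analysis day, separately for neutrophils and platelets. The sponsor should name the day before database lock; the documents give no basis for choosing one here.
3. Report time to engraftment as cumulative incidence, with death before engraftment as a competing event and censoring at the last contact at which engraftment status is known.
4. State that the exclusion in Protocol 9.3.1.3 does not apply to engraftment, and record this in SAP 9.1.

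Protocol 9.3 requires a protocol amendment for an analysis change only if site conduct alters, so SAP wording should be enough. With about 25 patients per arm, the count table is the essential part and a simple cumulative-incidence curve is sufficient beside it.

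The cost is slightly more analysis work and possibly a less favourable figure. Engraftment outcomes and survival are already collected. One check is needed: Appendix A says "additional transplant-related data will be collected following ASCT until time of engraftment" and gives no end point for patients who never engraft. The sponsor should confirm that the case report form records the last date on which such a patient's status was known.

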7.6.7 Deaths

The number of total deaths, deaths that occur within 30 days of last study treatment, and deaths that occur more than 30 days after last study treatment as well as the relationship to disease will be summarized. In addition, cause of death will be summarized by descending

MedDRA preferred term (unless otherwise specified). Death information will be listed by patient.

8 INTERIM ANALYSIS

A Safety Monitoring Committee (SMC) comprising the study investigators, medical monitor, and study biostatistician will monitor the trial for safety and dose delay toxicities (DDTs). For the planned safety reviews, enrollment will only be paused during the first safety review, unless required by the SMC. The SMC will review data for both treatment arms to include, but not be limited to, the following:

- Incidence of DDT
- Adverse events
- Clinical laboratory tests
- Response assessments, if available
- PBSC mobilization, if available

The SMC will review data for both treatment arms, and may make a recommendation

- Continue the trial as planned
- Modify the dose of denintuzumab mafodotin (e.g., to 2 mg/kg) in patients subsequently enrolled to the 19A+RICE Arm
- Temporarily halt enrollment

Two interim administrative evaluations of the overall safety and activity may be performed when approximately 40 and 75 patients have completed EOT. The hypothesis test that compares the CR rate of the 2 arms will not be performed. The activity data will be used for risk/benefit discussion. The study will not be discontinued unless there is a safety concern.

9 CHANGES FROM PLANNED ANALYSES

9.1 Changes from the Original Protocol

Not Applicable.

9.2 Changes from the Original SAP

Not Applicable.

Appendix A Imputation of Partially Unknown Adverse Event Dates

The algorithm below should be used to impute pre-existing condition and adverse event (AE) start dates for which only partial information is known. For ease of reading, both pre-existing conditions and AEs will be referred to as AE for the remainder of this document. The algorithm should be applied to every AE record on a record by record basis. AE start dates should be imputed before imputation of AE condition end date in all cases. The AE condition end date should only be used in the imputation of the AE start date if it is a complete, known date.

AE day and month are missing

- If the year is the same as the year of first dose of investigational agent and the onset period and/or onset time indicate that the start of the AE was pre-dose:
 - AE start date will be imputed as the minimum of (AE condition end date*, day prior to first dose of investigational agent)
- If the year is the same as the year of first dose of investigational agent and the onset period and/or onset time indicate that the start of the AE was post-dose:
 - AE start date will be imputed as the minimum of (AE condition end date*, first dose date of investigational agent)
- If the year is before the year of first dose of investigational agent:
 - AE start date will be imputed as the minimum of (AE condition end date*, December 31st see example 2 below)
- If the year is after the year of first dose of investigational agent:
 - AE start date will be imputed as the minimum of (AE condition end date*, January 31st see example 2 below)

AE month only is missing

- Treat day as missing and replace both month and day according to the above procedure

AE day only is missing

- If the month/year is the same as the month/year of first dose of investigational agent and the onset period and/or onset time indicate that the start of the AE was pre-dose:
 - AE start date will be imputed as the minimum of (AE condition end date*, day prior to first dose of investigational agent)
- If the month/year is the same as the month/year of first dose of investigational agent and the onset period and/or onset time indicate that the start of the AE was post-dose:
 - AE start date will be imputed as the minimum of (AE condition end date*, first dose date of investigational agent)
- If the month/year is before the month/year of first dose of investigational agent:

- AE start date will be imputed as the minimum of (AE condition end date*, last day of the month)
- If the month/year is after the month/year of first dose of investigational agent:
 - AE start date will be imputed as the minimum of (AE condition end date*, last day of the month)

* Only use condition end date if known and complete end date is available.

The following algorithm should be used to impute AE condition end dates. The AE records for a condition/event should be sorted by the imputed start dates then record position (order of entry into the eCRF). After sorting, if any condition end date month/year is greater than any subsequent record end date month/year, then change the imputed start day only to end of month. Repeat as necessary.

After sorting the AE records, apply the following rules to partial or missing AE condition end dates:

For all records excluding the last chronological record for a condition/event

- AE condition end date will be imputed as the start date of the subsequent record

For the last chronological record for a condition/event

- If outcome is “recovered/resolved”, ”recovered/resolved with sequelae”, or “fatal” apply the following:
 - If only year is provided for the end date and year is equal to the year of the last dose date:
 - AE condition end date will be imputed as the minimum of (last dose date+30, death date, data extraction date, December 31st of the end date year)
 - If only year is provided for the end date and year is not equal to the year of the last dose date:
 - AE condition end date will be imputed as the minimum of (death date, data extraction date, December 31st of the end date year)
 - If month and year are provided for the end date:
 - AE condition end date will be imputed as the minimum of (death date, data extraction date, last day of the end date month/year)
- If outcome is “recovering/resolving”, “not recovered/resolved”, “unknown”, or blank:
 - AE condition end date will not be imputed.

Example 1

AESPID 1: Condition/Event HEADACHE

First dose date 01JAN2012

Prior to imputation

Start date	Condition end date	Severity	Outcome	Onset
UNUNK2011	15APR2012	1	not recovered/resolved	pre-ICF
15APR2012	UNMAY2012	2	recovering/resolving	post 1st dose
UNMAY2012	UNJUN2012	1	not recovered/resolved	post 1st dose
UNJUN2012	UNJUN2012	3	recovering/resolving	post 1st dose
UNJUN2012	10JUL2012	2	recovering/resolving	post 1st dose
10JUL2012	--	1	not recovered/resolved	post 1st dose

Post imputation

Start date	Condition end date	Severity	Outcome
31DEC2011	15APR2012	1	not recovered/resolved
15APR2012	31MAY2012	2	recovering/resolving
31MAY2012	30JUN2012	1	not recovered/resolved
30JUN2012	30JUN2012	3	recovering/resolving
30JUN2012	10JUL2012	2	recovering/resolving
10JUL2012	--	1	not recovered/resolved

Example 2 (highlights choice of last day of the month as opposed to the 1st or the 15th)

AESPID 4: Condition/Event NAUSEA

First dose date 01APR2012

Prior to imputation

Start date	Condition end date	Severity	Outcome	Onset
UNUNK2011	25APR2012	1	not recovered/resolved	pre-ICF
25APR2012	UNAPR2012	2	recovering/resolving	post 1st dose
UNAPR2012	04MAY2012	1	recovered/resolved	post 1st dose

Post imputation

Start date	Condition end date	Severity	Outcome
31DEC2011	25APR2012	1	not recovered/resolved
25APR2012	31APR2012	2	recovering/resolving
31APR2012	04MAY2012	1	recovered/resolved

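### SAP Appendix A can date an adverse event's start after death, and fills a missing start day at opposite extremes depending on the calendar month

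*SAP*

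**What the plan says.** SAP section 6.5 gives the purpose of the imputation: "AE dates will be imputed for the purpose of calculating duration of events and treatment-emergent status". Appendix A then sets the start of a post-dose event with only the day missing:

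- First-dose month: "AE start date will be imputed as the minimum of (AE condition end date*, first dose date of investigational agent".
- Any later month: "AE start date will be imputed as the minimum of (AE condition end date*, last day of the month".
- The end date enters either minimum on one condition: "Only use condition end date if known and complete end date is available".

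The end-date rule for a last record that is resolved or fatal, with month and year known, does carry caps: "AE condition end date will be imputed as the minimum of (death date, data extraction date, last day of the end date month/year". No end date is imputed for a last record that is recovering, not recovered, unknown or blank.

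For conditions with several records, a re-sort step applies "if any condition end date month/year is greater than any subsequent record end date month/year, then change the imputed start day only", moving that day to month end. Example 2 is offered as the reason for month end; it "highlights choice of last day of the month as opposed to the 1st or the 15th".

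SAP section 7.6.1.1.1 uses these dates: "Time to onset and duration to improvement or resolution will be summarized at the patient level for ocular AEs". Ocular events are the only adverse events of special importance (section 7.6.1.1).

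**The concern.** There are three separate defects.

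1. A start date can fall after the patient's death or after data extraction, because the caps in the end-date rule are missing from the start-date rule.
2. The same gap in the data is filled with the earliest feasible day or the latest, depending only on the calendar month. Errors therefore run in opposite directions between months and, within a record, between onset and duration.
3. The re-sort step compares end months only, so it cannot repair records that end in the same month.

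At stake are ocular time to onset and time from first onset to improvement or resolution. No sensitivity analysis on imputed dates is planned.

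**Working it through.** **The SAP's own examples.** Applying the start rule, re-sort and end rule to Example 1 reproduces all six start dates and all five end dates. In Example 2 (first dose 01APR2012) the third record's start is first min(04MAY, 01APR) = 01APR2012. It then sorts ahead of a record ending in April while itself ending in May, so the re-sort moves it to month end, 30APR2012. The SAP prints 31APR2012, which is not a date.

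**Start after death.** First dose 03APR2017, start May 2017 (day unknown), no complete end date, death 10MAY2017.
- Start = 31MAY2017, which is 31 - 10 = 21 days after death.
- If the event is fatal with end May 2017 (day unknown), end = min(10MAY, extraction, 31MAY) = 10MAY2017.
- Duration by SAP section 6.4 (end - start + 1) = 10 - 31 + 1 = -20 days.

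The same happens for any such record in a month after the first-dose month, unless death falls on the last day of that month.

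**Direction and size, complete end date.** Assumptions, none from the documents: first dose uniform over a year, onset uniform on Days 8-63, event length exponential with mean 21 days, one record per event, start day missing. Simulation of 100,000 events:

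| Onset month | Share | Mean duration, imputed vs true | Mean onset day, imputed vs true |
|---|---|---|---|
| Later | 83% | 11.4 vs 21.6 | 49.7 vs 39.5 |
| First-dose | 17% | 35.7 vs 21.3 | 1 vs 15.4 |

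In later months 52% of these events become one-day events.

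Event length matters. With onset spread over 0-92 days after first dose, later-month onset is late, and duration short, by 5.6, 10.2 and 12.5 days for mean lengths of 7, 21 and 42 days.

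**End day also missing (same 0-92 day setting).** In later months both dates go to month end. Duration error is then only about -1 day, although onset stays about 16 days late. In the first-dose month duration is about 23 to 24 days too long.

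**Diluted over all records.** The net onset shift per affected single-event patient is 0.83 x (49.7 - 39.5) + 0.17 x (1 - 15.4) = 8.5 - 2.4 = about 6 days. If 5%, 10% or 20% of start days are missing (assumed), the mean shift is about 0.3, 0.6 or 1.2 days.

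**Same-month chain.** First dose 1 April. Record A: 10 April to April (day unknown), Grade 3, recovering. Record B: April (day unknown) to 28 April, Grade 1, recovered.
- B's start = min(28 April, 1 April) = 1 April, so B sorts before A.
- Both end months are April, so the re-sort does nothing.
- A is now the last record, and its outcome bars an end date.

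A condition that resolved on 28 April keeps an open Grade 3 record. Section 7.6.1.1.1 requires no ongoing Grade 3 or 4 event before improvement is counted.

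**The case against.** The strongest reply is that little of this reaches a reported number. Ocular onset is the patient's earliest event, and resolution requires that no ocular event be ongoing, so errors in single records are diluted. With two or three independent events per patient and the same missing shares, the mean onset shift is 0.3 days or less in absolute size. Protocol section 7.7.1.2 asks for onset and resolution dates, section 7.7.1.4 requires an onset date on every SAE report, and section 8.2 provides for queries. Month end was also a deliberate choice, illustrated by keeping records in order. All of this stands and limits the size. It does not excuse a rule that can return a start after death.

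A reader might go further in four ways that the documents do not support:

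- **That ocular toxicity will be materially misdescribed.** The share of missing start days is not given, and time from last 19A dose to improvement or resolution uses no event start date.
- **That treatment-emergent classification is corrupted.** Appendix B goes first to the onset-period field and uses the start date only if that field is missing.
- **That Example 1's Grade 3 record, 30JUN to 30JUN, shows the harm.** It is one severity segment of a longer condition, and collapsing it does not move first onset.
- **That a midpoint should simply replace the rule.** For 7-day mean events in later months a feasible-window midpoint gives 11.8 against 7.5 true days. Without the next record's start as a bound it can also reverse dates. A record running May to May (days unknown), followed by one starting 5 May, would start on 16 May and end on 5 May.

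**Conclusion.** The point holds in this limited form. The absence of death and extraction caps is a logic error at any frequency, although it needs a missing or partial end date as well as a missing start day. The opposite-direction bias is real for affected records with a complete end date: about 11 against 22 days in later months and 36 against 21 in the first-dose month, under the assumed 21-day mean length. The failure of the re-sort on same-month chains follows from a literal reading, in a constructed but possible case. The consequences are confined to descriptive ocular onset and duration summaries. CR, PFS and OS are unaffected, and treatment-emergent status largely so. The overall size cannot be fixed without the share of missing start days.

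**What to change.** Amend Appendix A before database lock, which SAP section 1 allows:

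1. Add death date, data extraction date and the next record's known start date to the minimum in the post-dose start rules. In the death example the start becomes min(31 May, 10 May) = 10 May and the fatal duration 10 - 10 + 1 = 1 day.
2. Do not let a start fall before the first dose date or the previous record's start.
3. When start months tie, order a condition's records by eCRF entry before imputing, and query any record whose feasible window is empty. In the chain above, B then starts on max(1 April, 10 April) = 10 April, A ends there, and the condition closes on 28 April.
4. Report ocular time to onset and duration with a sensitivity analysis that uses the midpoint of the feasible window or is restricted to complete dates. State how many records had an imputed start.
5. Correct 31APR2012 to 30APR2012, the date the existing rules give. Then re-run both examples under the amended text: if steps 2 and 3 are applied before the re-sort, the third start in Example 2 becomes max(01APR, 25APR) = 25APR2012. The SAP should state the order of operations.

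The cost is an appendix edit, slightly more programming and one additional descriptive table.
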